8. EFFICACY

Analyses of efficacy described in this section are the primary analyses of the efficacy endpoints, and pertain to the ITT population (i.e., all patients randomized in the study), unless otherwise specified. The trial includes endpoints following 2 years of treatment.

Stratification factors including tolvaptan use (yes/no) and screening ACR (≤ 300 mg/g, >300 mg/g) will only be used in the efficacy models as covariates if the category with the smallest number of patients comprise $>20\%$ of patients enrolled in the study. Continuous baseline eGFR will be included as a covariate instead of the categorical eGFR stratification factor. The following abbreviations are used in descriptions of the ANCOVA and MMRM analysis models:

Table 9. MODEL PARAMETER ABBREVIATIONS

Abbreviation	Model Term
BASE_eGFR	Baseline eGFR
*Tolv_STRAT	Concomitant tolvaptan use (yes, no)
*ACR_STRAT	Screening ACR (≤ 300 mg/g, >300 mg/g)
TRT	treatment group
TRT x VISIT	the interaction between treatment and time
VISIT	analysis visit used as time

* Tolvaptan use (yes/no) and screening ACR (≤ 300 mg/g, >300 mg/g) will only be used in the efficacy models as covariates if the category with the smallest number of patients comprises $>20\%$ of patients enrolled in the study.

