4.4. Randomization

Patients will be randomized 1:1 to either bardoxolone methyl or placebo. Randomization will be performed using an interactive web response system (IWRS) and will be stratified by eligibility eGFR category (30 to <60; ≥60 to 90 mL/min/1.73 m²), concomitant tolvaptan use (yes, no), and screening ACR (≤300 mg/g, >300 mg/g). Eligibility eGFR is the average of the screening eGFR visits. Patients randomized to placebo will remain on placebo throughout the study, undergoing sham titration.

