6.5.4.1. Prognosis of CKD by eGFR and Albuminuria Category

Prognosis of chronic kidney disease (CKD) is determined by the intersection of the following eGFR and albuminuria categories ([KDIGO, 2013](#)):

Figure 2: PROGNOSIS OF CKD BY eGFR AND ALBUMINURIA CATEGORIES

				Persistent albuminuria categories Description and range		
				A1	A2	A3
				Normal to mildly increased	Moderately increased	Severely increased
				<30 mg/g <3 mg/mmol	30–300 mg/g 3–30 mg/mmol	>300 mg/g >30 mg/mmol
GFR categories (ml/min per 1.73 m ²) Description and range	G1	Normal or high	≥90			
	G2	Mildly decreased	60–89			
	G3a	Mildly to moderately decreased	45–59			
	G3b	Moderately to severely decreased	30–44			
	G4	Severely decreased	15–29			
	G5	Kidney failure	<15			

Green: low risk (if no other markers of kidney disease, no CKD); yellow: moderately increased risk; orange: high risk; red, very high risk.

The Prognosis of Kidney Disease: Improving Global Outcomes (KDIGO) CKD progression risk scores is summarized by cell and color (Green, Yellow, Orange and Red).

Table 6. CKD STAGE

CKD ^a Stage	eGFR ^b (mL/min/1.73 m ²)
1	≥90
2	60 to <90
3a	45 to <60
3b	30 to <45
4	15 to <30
5	<15

^a Chronic kidney disease

^b Estimated glomerular filtration rate

Table 7. ALBUMINURIA CATEGORY

ACR ^a Category	ACR (mg/g)
1 (normo-albuminuria)	<30
2 (micro-albuminuria)	30 to ≤300
3 (macro-albuminuria)	>300

^a Urine albumin to creatinine ratio

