8.4. Primary Endpoint

8.4.1. Primary Endpoint Analysis

The primary endpoint of this study is the off-treatment change from baseline in eGFR at Week 108. The ITT population will be used for all analyses. For all patients enrolled in the trial, Week 108 is the off-treatment eGFR assessed closest to 108 weeks after Study Day 1. For a patient who completed 2 years of treatment, the 8-week drug treatment withdrawal period occurs at Week 108 (i.e., 56 days after last dose). For a patient who stopped drug treatment early, the eGFR assessment at Week 108 is analyzed, irrespective of how long a patient has been off-treatment. Analysis of Week 108 (after a planned 8-week drug treatment withdrawal period) assesses the preserved drug benefit (relative to placebo) following withdrawal of treatment.

The off-treatment change from baseline eGFR at Week 108 for patients treated with bardoxolone methyl is compared to placebo using an ANCOVA model, with BASE_eGFR as a covariate, and TRT as fixed effects. The ANCOVA analysis uses eGFR values collected in the Week 108 analysis window (Section 6.5.2), which includes the follow-up assessment at Week 108 for patients who discontinued treatment early irrespective of time after last dose.

Missing Week 108 eGFR data will not be imputed.

The difference between bardoxolone methyl and placebo in change from baseline of eGFR is estimated along with the 95% confidence interval at Week 108.

Example SAS code as follows:

```
proc glm data=efficacy;
  class TRT ACR_STRAT;
  model DELT_eGFR=trt ACR_strat base_egfr /solution;
  lsmeans trt / diff stderr pdiff cl alpha=0.05;
run;
```

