8.5.1. Secondary Efficacy Endpoint Analyses

The secondary efficacy endpoint of this study is the change from baseline in eGFR at Week 100 (i.e., the end of the first year of drug exposure). The change from baseline in eGFR for patients treated with bardoxolone methyl is compared with placebo at Week 100 using MMRM analysis, with BASE_eGFR as a covariate, and the following fixed factors: treatment group (TRT), time (i.e., VISIT; analysis visit number), and the interaction between treatment and time (TRT x VISIT).

The trial design separates discontinuation of study drug from discontinuation of study follow-up. Therefore, patients may discontinue early from study drug while continuing follow-up with study visits and assessments. The analysis of eGFR at Week 100 uses available eGFR values irrespective of whether or not a patient is receiving treatment. Analyses for Week 100 will not include the Week 52 data due to mix of on-treatment and off-treatment values. The MMRM analysis uses all eGFR values collected through Week 100 according to analysis visits 1, 2, 4, 6, 8, 12, 24, 36, 48, 64, 76, 88, and 100 (Section 6.5.2). An unstructured covariance matrix is used. In the event the MMRM model with an unstructured covariance structure does not converge, the following covariance structures are substituted, in the order listed. Each subsequent covariance structure is used only if each no previous model did not converge.

1. Heterogeneous Toeplitz covariance structure (assuming different variances at each time point and measurements taken closer together in time are more highly correlated than those taken farther apart).
2. Toeplitz covariance structure (assuming measurements taken closer together in time are more highly correlated than those taken farther apart).
3. First order auto-regressive [AR(1)] covariance structure (assuming measurements taken closer together in time are more highly correlated than those taken farther apart, but the correlation is more constrained than the Toeplitz structure).
4. Compound symmetry covariance structure (assuming equal correlation for measurements from a patient, regardless of how far apart in time they were taken).

If the MMRM model does not converge using any of the aforementioned covariance structures, variables from the model statement may be removed in the sequence of 1) Tolv_STRAT, 2) ACR_STRAT.

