The difference between bardoxolone methyl and placebo in change from baseline in eGFR is estimated along with the 95% confidence interval at Week 100 for the primary analysis of the secondary endpoint.

Missing eGFR data will not be imputed.

SAS example as follows:

```
proc mixed data=OUT2 method=reml alpha=0.05 covtest;  
  class VISITNUM(ref=LAST)  
        TRT(ref=FIRST) SUBJID ACR_STRAT;
```

```
model DELT_eGFR = BASE_eGFR ACR_STRAT TRT VISITNUM  
          TRT*VISITNUM BASE_eGFR*VISITNUM / solution ddfm=kr;  
repeated VISITNUM / subject=SUBJID type=un r;  
lsmeans TRT*VISITNUM / pdiff om cl e;  
estimate 'Estimate at Week 100' TRT 1 -1 TRT*VISITNUM 1 -1 / cl;  
ods output LSMeans=LSM diffs=Diff;
```

run;

[figure not shown]
A plot of least squared means from the MMRM model at each visit by treatment arm will be created.

[figure not shown]

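### SAP Section 8 drops the screening-ACR randomisation stratum from the efficacy models when its smaller category is 20% or less, while the example code fits it without condition: a small, avoidable loss of precision if ACR is prognostic

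*SAP*

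**What the plan says.** **Randomisation.** SAP Section 4.4 stratifies 1:1 allocation by eligibility eGFR category, "concomitant tolvaptan use (yes, no), and screening ACR" at a cut of 300 mg/g.

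**General rule for the models.** SAP Section 8 replaces the eGFR stratum with continuous baseline eGFR. It then says the tolvaptan and ACR strata "will only be used in the efficacy models as covariates if the category with the smallest number of patients comprise" more than 20% of those enrolled. The Table 9 footnote repeats the condition. No reason is given for the cut.

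**Primary ANCOVA (8.4.1).** The text describes the model "with BASE_eGFR as a covariate, and TRT as fixed effects". The example code directly below reads "model DELT_eGFR=trt ACR_strat base_egfr /solution".

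**Secondary MMRM (8.5.1).** The text lists baseline eGFR, treatment, visit and treatment-by-visit. The example code begins "model DELT_eGFR = BASE_eGFR ACR_STRAT TRT VISITNUM" and also carries a baseline-eGFR-by-visit term that is in neither the text nor Table 9. If the model does not converge, Tolv_STRAT and then ACR_STRAT may be removed.

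**Reach.** Section 8.6.1.2 reuses the 8.4.1 ANCOVA at Week 112. Section 8.3 makes every significance level nominal and descriptive.

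**The concern.** Read literally, the SAP describes the primary model in three ways: ACR if its smaller category is large enough (Section 8), no ACR (8.4.1 text), and ACR always (8.4.1 code). A reader cannot tell which one will produce the reported interval, because the SAP does not give the ACR split.

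The general rule is also the less efficient choice. Stratified allocation balances the arms on ACR. If ACR is related to the outcome and is left out, its between-stratum variance stays in the residual. The reported standard error then exceeds the true sampling SD, the interval is a little too wide and the test a little conservative. Once Week 108 values are missing, the balance is no longer exact and some real precision is lost as well. With inference descriptive, the 95% CI is the main output, so its width and its model are what is at stake. The treatment estimate is not biased.

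**Working it through.** **Inputs from the SAP (4.3.1, 4.4).** N=850 allocated 1:1, so 425 per arm; SD of change 12; difference 2.3; two-sided alpha 0.05; stated power about 80%.

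**The plan's own figure.** SE = 12 × √(2/425) = 0.823. A two-sample calculation with difference 2.3 gives 79.8% power (79.7% with the noncentral t), so the stated 80% reproduces.

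**Inputs the documents do not give (assumed).**
- p, share of the smaller ACR category: 2% to 20%, the range in which the rule drops the term.
- d, gap between ACR strata in mean eGFR change after baseline eGFR: 0 to 6 mL/min/1.73 m².
- q, share of patients with a Week 108 value: 100%, or a random 40% (340 patients). The second case is included because SAP Section 2 reports that development stopped, with sites told on 10 May 2023, and Section 8.4.1 states "Missing Week 108 eGFR data will not be imputed".

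**Change in the reported SE.** The share of variance due to the stratum is f = p(1−p)d²/12². The ratio of SE with ACR_STRAT to SE without it is √(1−f).
- p=0.10, d=4: f = 0.09 × 16/144 = 0.010; ratio 0.995, so 0.5% narrower.
- p=0.20, d=6: f = 0.16 × 36/144 = 0.040; ratio 0.980, so 2.0% narrower.
- d=0: f = 0, no gain.

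**How far the omitted-stratum SE overstates the truth.** With stratified allocation and a random share q observed, n values per arm, the true variance of the estimate without ACR_STRAT is (2/n) × 144 × (1−fq), against a reported (2/n) × 144. The excess is 1/√(1−fq) − 1. The type I error is 2 × [1 − Φ(1.96/√(1−fq))].

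| p, d | q | SE excess | Type I error |
|---|---|---|---|
| 0.10, 4 | 1.0 | 0.5% | 0.0489 |
| 0.10, 4 | 0.4 | 0.2% | 0.0495 |
| 0.20, 6 | 1.0 | 2.1% | 0.0455 |
| 0.20, 6 | 0.4 | 0.8% | 0.0482 |

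With complete data, nearly all of the loss is an overstated SE. With 40% observed, part is real imprecision. At p=0.20, d=6 the true SD ratio of adjusted to unadjusted estimate is √(0.960/0.984) = 0.988, about 1.2%, and the other 0.8% is overstatement.

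**CI half-width at p=0.20, d=6.**
- N=850: 1.96 × 0.823 = 1.61 without ACR_STRAT; × 0.980 = 1.58 with it.
- 340 observed: SE = 12 × √(2/170) = 1.302; half-width 2.55 without, 2.50 with.

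**On the power scale (N=850, d from 2 to 8).** Replacing 12 by 12√(1−f) raises power from 79.8% to 79.8–80.6% at p=5%, 79.9–81.4% at p=10%, and 80.0–82.6% at p=20%. For d up to 4 the gain is at most 0.7 points.

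**Simulation check** (least squares with a baseline covariate, stratified allocation). At p=0.20, d=6 the SE ratio is 0.980 with complete data (100,000 runs) and 0.981 with 40% observed (200,000 runs). The type I errors are 0.045 and 0.047 without ACR_STRAT, and 0.0495 and 0.049 with it.

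**Cost of keeping the term.** At p=0.02 with 340 observed, the SE is about 0.1% wider at d=0 and 0.07% wider at d=2. The ACR >300 mg/g stratum is empty in 0.02% of runs. Sparsity is therefore a weak reason for the cut: even 5% of 850 is about 42 patients, and the term is a single main effect.

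**The case against.** The rule is explicit, pre-specified and stated twice, and the programs are labelled as examples. Section 8 can be read as governing, with the 8.4.1 and 8.5.1 text as shorthand; the convergence fallback fits that reading. Both programs include ACR_STRAT and omit Tolv_STRAT, which is what the rule would give if ACR had already passed 20% and tolvaptan had not. The SAP is dated after the decision to stop development, and a pooled stratum count needs no unblinding. On that reading nothing is lost.

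This is possible, but the documents do not say it. If it is so, deleting the condition changes nothing in the analysis and removes the ambiguity. If it is not so, code run as printed departs from the written rule.

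A second objection has more force. The support for ACR as prognostic is thin. Section 6.5.4.1 says "Prognosis of chronic kidney disease (CKD) is determined by the intersection of the following eGFR and albuminuria categories", but that is a general CKD risk grid used to describe baseline status. It does not show that ACR predicts two-year eGFR change in ADPKD after adjustment for baseline eGFR. The gain is therefore conditional on an effect the documents do not quantify.

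It is also true that the loss is small, in the conservative direction, and bears on no confirmatory decision. The protocol (12.3.1) requires only treatment and baseline eGFR and leaves other covariates to the SAP, so there is no protocol conflict.

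**Conclusion.** The point holds as a minor one. Section 8 can remove a factor the trial randomises by, and the example code does not apply that condition. Over the assumed range (share 2–20%, gap 0–6, SD 12) the reported SE would be between 0 and about 2% larger than necessary, with type I error between 0.0455 and 0.05. These figures are for the ANCOVA. They rest on an assumed ACR split, an assumed prognostic gap, the planned rather than actual N and, for the reduced sample, values missing at random. There is no loss if ACR is not prognostic or if its smaller category exceeds 20%. Keeping the term costs at most about 0.1% in SE in the cases examined, so the balance favours keeping it. The unlisted baseline-eGFR-by-visit term is a separate editorial mismatch that can be corrected in the same edit.

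**What to change.** - In SAP Section 8 and the Table 9 footnote, delete the 20% condition for ACR_STRAT.
- State the primary ANCOVA as TRT + BASE_eGFR + ACR_STRAT, as the 8.4.1 code already has it. Week 112 follows automatically.
- State the MMRM as TRT + VISIT + TRT × VISIT + BASE_eGFR + BASE_eGFR × VISIT + ACR_STRAT, as in the 8.5.1 code, and add the baseline-by-visit term to Table 9.
- Bring the 8.4.1 and 8.5.1 text into line with these models.
- The 20% rule can stay for Tolv_STRAT, because patients on tolvaptan remain only if enrolled under Version 2 (protocol 9.3.1.1). The convergence fallback can stay as written.

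The cost is SAP wording, to be settled before database lock, and one model degree of freedom. No new data or assessments are needed.

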8.1. General Considerations

Data collected from individual study centers will be pooled; results will not be presented by individual study center. Analyses are performed for all bardoxolone methyl patients in comparison with all placebo patients. Summary statistics for observed values, change from baseline, and percent change from baseline are presented by randomized treatment group. Missing values are handled as described in Section 6.6.

8.2. Statement of the Null and Alternate Hypotheses

All primary efficacy analyses compare the change from baseline in eGFR for patients randomized to bardoxolone methyl ($\Delta_{\text{eGFR_BARD}}$) to the change from baseline in eGFR for patients randomized to placebo ($\Delta_{\text{eGFR_PBO}}$) at the endpoint-specified visit according to the following hypotheses:

- Null hypothesis, $H_0: (\Delta_{\text{eGFR_BARD}}) - (\Delta_{\text{eGFR_PBO}}) = 0 \text{ mL/min/1.73 m}^2$
- Alternative hypothesis, $H_1: (\Delta_{\text{eGFR_BARD}}) - (\Delta_{\text{eGFR_PBO}}) \neq 0 \text{ mL/min/1.73 m}^2$

Because eGFR decreases with disease progression, a higher change from baseline in eGFR for bardoxolone methyl relative to placebo is considered evidence of benefit.

8.3. Multiple Comparisons and Multiplicity

All objectives are presented with nominal significance levels for descriptive purposes only.

8.4. Primary Endpoint

8.4.1. Primary Endpoint Analysis

The primary endpoint of this study is the off-treatment change from baseline in eGFR at Week 108. The ITT population will be used for all analyses. For all patients enrolled in the trial, Week 108 is the off-treatment eGFR assessed closest to 108 weeks after Study Day 1. For a patient who completed 2 years of treatment, the 8-week drug treatment withdrawal period occurs at Week 108 (i.e., 56 days after last dose). For a patient who stopped drug treatment early, the eGFR assessment at Week 108 is analyzed, irrespective of how long a patient has been off-treatment. Analysis of Week 108 (after a planned 8-week drug treatment withdrawal period) assesses the preserved drug benefit (relative to placebo) following withdrawal of treatment.

The off-treatment change from baseline eGFR at Week 108 for patients treated with bardoxolone methyl is compared to placebo using an ANCOVA model, with BASE_eGFR as a covariate, and TRT as fixed effects. The ANCOVA analysis uses eGFR values collected in the Week 108 analysis window (Section 6.5.2), which includes the follow-up assessment at Week 108 for patients who discontinued treatment early irrespective of time after last dose.

Missing Week 108 eGFR data will not be imputed.

The difference between bardoxolone methyl and placebo in change from baseline of eGFR is estimated along with the 95% confidence interval at Week 108.

Example SAS code as follows:

```
proc glm data=efficacy;
  class TRT ACR_STRAT;
  model DELT_eGFR=trt ACR_strat base_egfr /solution;
  lsmeans trt / diff stderr pdiff cl alpha=0.05;
run;
```

8.5. Secondary Efficacy Endpoint

The ITT population will be used for all analyses unless otherwise specified.

8.5.1. Secondary Efficacy Endpoint Analyses

The secondary efficacy endpoint of this study is the change from baseline in eGFR at Week 100 (i.e., the end of the first year of drug exposure). The change from baseline in eGFR for patients treated with bardoxolone methyl is compared with placebo at Week 100 using MMRM analysis, with BASE_eGFR as a covariate, and the following fixed factors: treatment group (TRT), time (i.e., VISIT; analysis visit number), and the interaction between treatment and time (TRT x VISIT).

The trial design separates discontinuation of study drug from discontinuation of study follow-up. Therefore, patients may discontinue early from study drug while continuing follow-up with study visits and assessments. The analysis of eGFR at Week 100 uses available eGFR values irrespective of whether or not a patient is receiving treatment. Analyses for Week 100 will not include the Week 52 data due to mix of on-treatment and off-treatment values. The MMRM analysis uses all eGFR values collected through Week 100 according to analysis visits 1, 2, 4, 6, 8, 12, 24, 36, 48, 64, 76, 88, and 100 (Section 6.5.2). An unstructured covariance matrix is used. In the event the MMRM model with an unstructured covariance structure does not converge, the following covariance structures are substituted, in the order listed. Each subsequent covariance structure is used only if each no previous model did not converge.

1. Heterogeneous Toeplitz covariance structure (assuming different variances at each time point and measurements taken closer together in time are more highly correlated than those taken farther apart).
2. Toeplitz covariance structure (assuming measurements taken closer together in time are more highly correlated than those taken farther apart).
3. First order auto-regressive [AR(1)] covariance structure (assuming measurements taken closer together in time are more highly correlated than those taken farther apart, but the correlation is more constrained than the Toeplitz structure).
4. Compound symmetry covariance structure (assuming equal correlation for measurements from a patient, regardless of how far apart in time they were taken).

If the MMRM model does not converge using any of the aforementioned covariance structures, variables from the model statement may be removed in the sequence of 1) Tolv_STRAT, 2) ACR_STRAT.

The difference between bardoxolone methyl and placebo in change from baseline in eGFR is estimated along with the 95% confidence interval at Week 100 for the primary analysis of the secondary endpoint.

Missing eGFR data will not be imputed.

SAS example as follows:

```
proc mixed data=OUT2 method=reml alpha=0.05 covtest;  
  class VISITNUM(ref=LAST)  
        TRT(ref=FIRST) SUBJID ACR_STRAT;
```

```
model DELT_eGFR = BASE_eGFR ACR_STRAT TRT VISITNUM  
          TRT*VISITNUM BASE_eGFR*VISITNUM / solution ddfm=kr;  
repeated VISITNUM / subject=SUBJID type=un r;  
lsmeans TRT*VISITNUM / pdiff om cl e;  
estimate 'Estimate at Week 100' TRT 1 -1 TRT*VISITNUM 1 -1 / cl;  
ods output LSMeans=LSM diffs=Diff;
```

run;

[figure not shown]
A plot of least squared means from the MMRM model at each visit by treatment arm will be created.

[figure not shown]

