Most recently, bardoxolone methyl was studied in a Phase 2 trial (study 402-C-1702, PHOENIX, NCT03366337) in patients with four rare forms of CKD: genetically-confirmed autosomal dominant polycystic kidney disease (ADPKD), biopsy-confirmed IgA nephropathy (IgAN), diabetic nephropathy secondary to type 1 diabetes (T1D), or biopsy-confirmed focal segmental glomerulosclerosis (FSGS). In the cohort of patients with ADPKD with PKD1 mutations, treatment with bardoxolone methyl significantly increased eGFR after treatment with 12 weeks (mean ± SE: 9.3 ± 1.4 mL/min/1.73 m^2; n=31; p<0.0001). The improvements were consistent, and 27 of the 28 (96%) patients with data at Week 12 had improvements from baseline in eGFR. The increases were observed across multiple subgroups including age, gender, baseline eGFR, and baseline albumin to creatinine ratio (ACR). Historical eGFR data for 29 of the 31 patients showed that these patients' kidney function was declining at an average annual rate of 4.8 mL/min/1.73 m^2 prior to study entry. Therefore, the improvements in eGFR after 12 weeks of treatment with bardoxolone methyl represents a recovery of approximately two years of average eGFR loss in ADPKD patients. Thus, the magnitude and durability of eGFR increases with bardoxolone methyl could provide a meaningful therapeutic benefit, even over the sole available therapy (tolvaptan) in ADPKD.

**Table 3: Cross-Study Comparison of Increases in eGFR, Inulin Clearance, and Creatinine Clearance with Bardoxolone Methyl Treatment**

Study	Phase/ Country	Study Population	# of Patients	Treatment Duration	$\Delta$ eGFR (mL/min/1.73m  ) a
CKD Studies					
402-C-0801 (Stratum 1) (open label)	2a/ US	Age $\geq$ 18, Diabetic nephropathy	60	28 days	6.7 (p<0.001)
402-C-0801 (Stratum 2) (open label)	2b/ US	Age $\geq$ 18, Diabetic nephropathy	20	56 days	7.2 (p<0.001) CrCl also sig. increased
402-C-0804 (BEAM)	2/ US	Age $\geq$ 18, T2D and CKD	227	52 weeks	8.6 at WK52 (p<0.001 vs PBO)
402-C-0902	2/ US	Age $\geq$ 18, T2D and CKD	131	85 days	6.5 (p<0.001)
402-C-0903 (BEACON)	3/ Global	Age $\geq$ 18, T2D and Stage 4 CKD	2185	Median: 7 months with 522 patients through Week 48	6.4 (p<0.001 vs PBO) CrCl also significantly increased
402-C-1102	1/US	Age $\geq$ 18, T2D and Stage 3b and Stage 4 CKD	24	56 days	9.0 (p<0.05)
RTA402-005 (TSUBAKI)	2/ Japan	Age $\geq$ 20, T2D and Stage 3 and 4 CKD	120	16 weeks	6.6 (inulin GFR) (p=0.008 vs PBO)

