4.3. Sample Size Considerations

4.3.1. Primary Endpoints

With 850 patients enrolled, the study will have approximately 80% power to detect a difference between the 2 treatment groups in change from baseline eGFR of 2.3 mL/min/1.73 m². The power calculation was based on a 2-sample t-test as an estimate for the planned analysis of covariance (ANCOVA) analysis and assumes the following:

- Overall two-sided Type I error rate total of 0.05;
- Standard deviation of change from baseline in eGFR of 12 mL/min/1.73 m²;
- Analyses are based on the intent-to-treat (ITT) population;
- Missing data will be imputed using multiple imputation.

PASS 13 software was used to calculate sample size.

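### SAP 8.5.1: fallback covariance structures 2 to 4 pool one variance over 13 visits with no robust standard error, so the Week 100 interval could be too narrow if two earlier models fail to converge

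*SAP*

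**What the plan says.** SAP 8.5.1 compares the arms at Week 100 with an MMRM on analysis visits 1, 2, 4, 6, 8, 12, 24, 36, 48, 64, 76, 88 and 100, using an unstructured covariance matrix. If it does not converge, "the following covariance structures are substituted, in the order listed":

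1. "Heterogeneous Toeplitz covariance structure (assuming different variances at each time point", with correlation falling with separation;
2. "Toeplitz covariance structure (assuming measurements taken closer together in time are more highly correlated than those taken farther apart"), with one variance shared by all visits;
3. "First order auto-regressive [AR(1)] covariance structure", a more constrained version of the same idea;
4. "Compound symmetry covariance structure (assuming equal correlation for measurements from a patient, regardless of how far apart in time they were taken").

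Only item 1 carries visit-specific variances. The example code has "repeated VISITNUM / subject=SUBJID type=un r", Kenward-Roger degrees of freedom and no empirical option. It is written for the unstructured case. No code is given for the fallbacks, and the text names no standard-error method for them. SAP 8.3 reports all objectives at nominal levels, for description only.

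**The concern.** A covariance fallback is a contingency rule, so its interval should be valid when the rule is used. Items 2 to 4 estimate one variance from all 13 visits. Weeks 1, 2, 4, 6, 8 and 12 supply six of them. If patients' eGFR changes spread out over two years, those early visits pull the pooled variance below the Week 100 variance, and a model-based standard error inherits the shortfall.

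Two figures in the documents make growth plausible. Protocol 5.1.1 gives the Phase 2 ADPKD result at Week 12 as "mean ± SE: 9.3 ± 1.4", while SAP 4.3.1 plans on "Standard deviation of change from baseline in eGFR of 12" for the primary endpoint at about two years. At stake is the width of one reported interval. With significance levels purely nominal, the estimate and its interval are what readers will use.

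**Working it through.** **The plan's own figure.** With 425 per arm, SD 12 and difference 2.3 (SAP 4.3.1), SE = 12 × √(2/425) = 0.823. Then 2.3/0.823 = 2.79, 2.79 − 1.96 = 0.83, and Φ(0.83) = 0.80. The stated power of about 80% is reproduced. The documents give no figure for the MMRM fallbacks.

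**Early SD.** Phase 2 SE 1.4 with n = 28 to 31: 1.4 × √28 = 7.4 and 1.4 × √31 = 7.8. This assumes that the reported SE is a simple SD/√n.

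**Compound symmetry by hand, complete data.** The fitted common variance is the mean of the 13 visit variances. Hold the SD at 7.8 through Week 12 and let it rise linearly to 12 at Week 100:
- Weeks 1 to 12: 6 × 60.84 = 365.0.
- Weeks 24, 36, 48, 64, 76, 88, 100: 70.1 + 80.0 + 90.6 + 105.7 + 117.8 + 130.6 + 144.0 = 738.8.
- Mean = (365.0 + 738.8)/13 = 84.9, so fitted SD = 9.2.
- SE ratio at Week 100 = 9.2/12 = 0.77. Coverage = 2Φ(1.96 × 0.77) − 1 = about 87%.

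**Other starting values, variance linear in week.** The mean visit week is 469/13 = 36.1, and (36.1 − 1)/99 = 0.354.
- SD 7.5 to 12: 56.25 + 0.354 × 87.75 = 87.3; SD 9.35; ratio 0.78; coverage 87%. The 95% half-width is 1.96 × 9.35 × √(2/425) = 1.26, against 1.96 × 0.823 = 1.61.
- SD 8 to 12: 64 + 0.354 × 80 = 92.3; SD 9.61; ratio 0.80; coverage 88%.
- SD 10 to 12: 100 + 0.354 × 44 = 115.6; SD 10.75; ratio 0.90; coverage 92%.

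Complete-data likelihood fits of AR(1) and compound symmetry give 0.81 to 0.82 for 8 to 12 and 0.90 to 0.91 for 10 to 12, depending on the shape of the rise.

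**All four fallbacks, with dropout.** Each structure was fitted at its large-sample likelihood limit, and the model-based SE at Week 100 was compared with the true SE. Assumptions: correlation decaying with real time, as 0.95·exp(−d/200) or 0.85·exp(−d/100) with d in weeks, and 0, 20 or 40% missing by Week 100. The constant-SD column was run under the first correlation only.

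| Structure | SD 7.5 to 12: ratio (coverage) | Constant SD 12: ratio |
|---|---|---|
| Heterogeneous Toeplitz | 1.06–1.13 (96–97%) | 1.10–1.13 |
| Toeplitz | 0.75–0.81 (86–89%) | 0.97–1.00 |
| AR(1) | 0.77–0.80 (87–88%) | 1.00–1.01 |
| Compound symmetry | 0.70–0.78 (83–87%) | 0.91–1.00 |

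**Visit-order lag.** Repeating on VISITNUM makes Weeks 1–2 and Weeks 48–64 both lag 1, although they are 1 and 16 weeks apart. The constant-SD column isolates the misfit in correlation. Toeplitz and AR(1) are nearly unharmed. Compound symmetry, which uses no lag, loses a little under dropout. The common variance drives the shortfall.

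**The case against.** A reader might infer that every fallback assumes equal variances, so that failure of the unstructured model alone makes the interval too narrow. The SAP does not support that. Heterogeneous Toeplitz comes first, and in these scenarios it errs slightly wide. The harm needs both models to fail. The unstructured matrix has 13 × 14/2 = 91 parameters, and heterogeneous Toeplitz has 13 + 12 = 25, with no evident reason for it to fail. SAP Section 2 records that sites were told on 10 May 2023 that development had stopped, which may thin late visits, but the documents do not quantify this.

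It is also tempting to say that the documents show the variance growing. They do not. The Week 12 SE comes from a small cohort with PKD1 mutations. The SD of 12 is a planning value for the off-treatment primary endpoint, which the Protocol's Version 6 summary of changes bases on Week 104 data from Study 1603 and a longer off-treatment period. It is not a Week 100 SD. Steeper paths starting from 5 give lower ratios, but 5 has no source in the documents and is left out of the verdict.

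Finally, an inflated Type I error could be claimed, but under SAP 8.3 no confirmatory decision rests on this test. These points limit likelihood and consequence. What stands against the plan is that items 2 to 4 share one variance and that no robust standard error backs them up.

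**Conclusion.** The point holds in conditional form. If both the unstructured and the heterogeneous Toeplitz models fail, and if the SD of eGFR change grows over time, the Week 100 interval from items 2 to 4 would be too narrow. For an SD of about 7.5 to 8 rising to 12, the SE ratio is about 0.70 to 0.82 and coverage about 83 to 89%. For 10 rising to 12, the ratio is about 0.90 and coverage about 92 to 93%. With a constant SD, Toeplitz and AR(1) show almost no problem.

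This rests on the assumed SD path, correlations and dropout, and on model-based errors carrying over from the example code to the fallbacks. Visit-order lag should not be read as the cause. The Week 108 primary ANCOVA is unaffected. Low priority: a secondary endpoint, nominal levels, and a trigger whose probability the documents do not give.

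**What to change.** In SAP 8.5.1:
- Keep heterogeneous Toeplitz as the first fallback.
- Replace items 2 to 4 with heterogeneous-variance versions: ARH(1), then CSH.
- For any fallback, state that the empirical (sandwich) standard error is used with between-within degrees of freedom, in place of Kenward-Roger.

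The cost is a short rewrite of the list and a change of procedure options. Nothing changes if the unstructured model converges. Intervals would be somewhat wider where items 2 to 4 would otherwise have been used. The sandwich estimator corrects the width of the interval; it does not remove any bias in the estimate from a misspecified covariance under dropout.
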